4. SELECTION AND ENROLLMENT OF PARTICIPANTS

SOP: Patients will be assessed at screening and at baseline prior to the initiation of the intervention and biweekly thereafter until 12 weeks, and monthly between 3 and 6 month follow-up. There will also be a final Month 12 follow-up. If unable to schedule this final follow-up, participant will follow-up at Month 24 instead. Those who meet criteria after a telephone screening, will be invited for an in-person screening interview that may be split into 1-3 visits to accommodate clinical, neuropsychological, MRI and laboratory procedures. Baseline assessment (“Baseline 2”) will be performed within 2 months of the start of the interventions. The informed consent form will be reviewed with the participant, and signed prior to initiation of the assessments. Inclusion and exclusion criteria will be reviewed using the inclusion/exclusion

criteria form completed as a source document at screening, baseline, and prior to the first day of TCC and HEW classes.

4.1 Inclusion Criteria

Inclusion criteria: All 220 participants will have major depression and will 1) be on stable treatment for at least 4 months and still meet criteria for major depression; 2) Have a 24-item Hamilton Rating Scale for Depression (HAMD) score of > 14 at baseline consistent with moderate-severe depression; and 3) Have a Mini-Mental State Exam (MMSE) score > 24.

4.2 Exclusion Criteria

Exclusion criteria: subjects will be excluded if they had any current other psychiatric disorders (except for frequently comorbid anxiety symptoms or insomnia), are receiving effective antidepressant and psychotropic medications or psychotherapy; or have had recent unstable medical or neurological disorders (myocardial infarction within past 6 month, surgery within last 3 months); any disabilities preventing their participation in TCC exercise per PI's discretion; prior experience with practicing a mind-body intervention (defined as Tai Chi, Tai Chi Chih, yoga, meditation) or have practiced it at least weekly within the past 12 months; diagnosis of dementia; those with metal implants that contraindicate brain imaging. Please see Tables 1 and 3 for detailed *assessment schedules*.

Exclusion criteria for fMRI: 1) acute medical and neurological illness 2) evidence of metal in the body; 3) claustrophobia; 4) decline consent. Subjects that are only excluded from the fMRI portion of the study are allowed to remain in the study.

4.3 Study Enrollment Procedures

Recruitment of Subjects. Subjects will be recruited, assessed and randomized according to the scientific protocol and the consent procedures approved by the UCLA Institutional Review Board and the Office of Protection of Research Subjects, as well as the analogous units at participating institutions (e.g., Motion Picture and Television Fund). We project a recruitment period of 4.4 years to achieve a study group of **220 subjects**. With the anticipated average of about 4 subjects/month. The incentive to participate appears sufficient since the proposed project offers free TCC and HEW classes to every enrolled patient. In addition, two additional avenues are being developed, such as collaboration with the LA County Department of Mental Health.

We project our minority recruitment at 30%. If the rate of recruitment is not sufficient through the UCLA clinical and research services, advertising in local newspapers will be used. Recruitment through local support groups for depressed patients will also be attempted. [name] also has links to the local community of care providers for the elderly and to mental health professionals, who could serve as a source of referrals. She serves as a Consultant to the LA County Department of Mental Health Services for older adults, an outreach program which should help recruit minority participants. The anticipated rate of recruitment is 39 subjects in year 1 and 40 in year 5 and **47 subjects per year in years 2-4** to accommodate 12/24-month follow-up, a realistic rate for our study. Data analysis will be performed in year 5. We anticipate the dropout to be about **10% in the first 12 weeks, and additional 20 % at 12/24 months**.

Retention of subjects. We have used successful strategies for retention of elderly subjects with depression. These include an ongoing and continuous process of consent to study procedures, involvement of family members whenever possible, and use of concerned and empathic clinicians and staff. However, it is important to note that our data analytic approach is robust to attrition.

Cohort maintenance. The comprehensive evaluation of subjects prior to randomization and entry into the treatment trial is designed to minimize the risk of attrition. The evaluation of weekly compliance questionnaires will also alert the PI to potential attrition problems.

Table 1. Timeline.

Years of the project	ACTIVITIES
Year 1 (1-3 months)	Review assessment instruments with research assistant, research nurse; Inter-rater reliability sessions. Develop patient schedule with the UCLA CTSI. Develop patient database and databooks. Start subject recruitment at month 4.
Year 1 (4-12 months)	Review and maintain accuracy of databooks. Develop database (with research assistant and [name]) (recruit 39 subjects). DSMC meets every 6 months after recruitment starts.
Year 2	Continue recruitment (47 subjects). Conduct inter-rater reliability sessions. DSMC meets every 6 months.
Year 3	Recruit 47 subjects. Conduct inter-rater reliability sessions. DSMC meets every 6 months.
Year 4	Recruit 47 subjects. Conduct inter-rater reliability sessions. DSMC meets every 6 months
Year 5	Recruit 40 subjects in the first 6 months. Continue 6 month follow-up. Anticipate completion of final subject by month 10. DSMC meets once. Complete data analysis (months: 10-12).

Table 2. TARGETED / PLANNED ENROLLMENT: Number of Subjects 220

Ethnic Category	Sex/Gender		
	Females	Males	Total
Hispanic or Latino	10	6	16
Not Hispanic or Latino	130	74	204
Ethnic Category Total of All Subjects*	140	80	220
Racial Categories			
American Indian/Alaska Native	1	1	2
Asian	10	8	18
Native Hawaiian or Other Pacific Islander	1	1	2
Black or African American	10	6	16
White	118	64	182
Racial Categories: Total of All Subjects *	140	80	220

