1. STUDY OBJECTIVES

1.1 Primary Objective

Aim 1: Evaluate the effects of **TCC** versus **HEW** on reduction of depressive symptoms and improvement in the secondary outcomes during the 12-week treatment trial, in addition to 6 and 12 month follow-up (or 24 months if 12 months have passed).

Hypothesis 1: Compared to **HEW**, **TCC** will result in a) greater reduction of depressive symptoms and b) improvement in the cognitive domains of executive function and memory at 12 weeks, 6 months, and 12-month follow-up (or 24 months if 12 months have passed).

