9.2 Sample Size and Randomization

Power and sample size estimate: We assume that dropout will be at 10% and 20% at the end of 12 week treatment phase and 6 and 12 month follow-up, respectively. For Aim 1, if the treatment main effects are linear over the 12 week treatment phase on HAMD, our design with 7 time points (baseline, 2, 4, 6, 8, 10, 12 weeks) and with complete data on 99 subjects within each arm (10% dropout) will have 80% power at significance level $\alpha=0.05$ for detecting a treatment and time interaction corresponding to no difference at baseline and a difference of $d = 0.32$ SDs between any two arm at the end follow-up. Our R21 project found an effect size of 0.65 in HAMD between TCC and HEW at 12 weeks. If treatment effects continue to grow linearly over the 6 and

12 month follow-up, our design with complete data on 88 subjects within each arm (20% dropout) will have 80% power at significance level $\alpha=0.05$ for detecting a group difference between any two arms of $d = 0.36$ SDs at 6 and 12 month follow-up. The reported power is based on number of subjects with complete data, and hence is a conservative estimate of the actual power of our design, since the proposed GLMM framework utilizes all observed data collected from all subjects. In addition, the reported power analysis is based on a correlation of 0.5 between measurements obtained at different time points. Selection of the covariance structures within the GLMM model will be based on likelihood ratio test and/or AIC (Akaike Information Criterion). If we find either significant interactions or main effects, follow-up contrasts will be used to determine at which time points there has been significant change and/or differences in treatment effects relative to baseline.

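### The Table 1 calendar leaves about 22% of subjects (18% at the very least) unable to reach month 12, so the stated 12-month follow-up and 88 complete cases per arm cannot be met

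*Combined protocol and SAP*

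**What the plan says.** **Recruitment and calendar (section 4.3).** The text states: "We project a recruitment period of 4.4 years to achieve a study group of" 220 subjects. The yearly figures are 39 in year 1, 47 in each of years 2-4 and 40 in year 5, a rate said to be chosen "to accommodate 12/24-month follow-up, a realistic rate for our study. Data analysis will be performed in year 5". Table 1 opens recruitment in the fourth month of year 1 ("Start subject recruitment at month 4"). Its year 5 entry reads "Recruit 40 subjects in the first 6 months. Continue 6 month follow-up. Anticipate completion of final subject by month 10", with analysis placed in months 10-12. Table 1 does not mention 12-month follow-up.

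**Use of month 12.** Hypothesis 1 (section 1.1) covers depressive symptoms and "improvement in the cognitive domains of executive function and memory at 12 weeks, 6 months, and 12-month follow-up". Aim 3 (section 1.2) also rests on follow-up at 6 and 12 months. Section 9.5 schedules all outcome measures at 12 months.

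**Power (section 9.2).** The 12-month detectable difference of 0.36 SD at 80% power rests on "our design with complete data on 88 subjects within each arm (20% dropout" being the only loss deducted. The Sample Size and Population paragraph gives the same 88 completers per group.

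**A conflicting rule (section 6, Study Procedures).** This section says that the month 12/24 visit was added to the study later and is attended only by participants in the MRI portion. Sections 6 and 6.2.1 put that group at 55 per arm.

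**The concern.** Recruitment lasting 4.4 years followed by 12 months of follow-up takes 5.4 years, yet analysis is placed inside year 5. The claim about follow-up and the calendar cannot both stand.

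Two things are at stake. First, month-12 visits that fall after the data cut are lost in addition to dropout, so the month-12 sample size and detectable difference in section 9.2 are too favourable. Second, section 9.6 plans to compare drop-out rates, times and reasons between arms and to run a pattern-mixture sensitivity analysis. The plan does not distinguish a visit that the calendar cut off from one missed because the subject left. The reason list in sections 7.3 and 9.4 has no administrative category other than a residual one. If late recruits were coded as dropouts, those analyses would partly describe the calendar.

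**Working it through.** **Inputs.** From section 4.3 and Table 1: 39 subjects in project months 4-12, 47 in each of years 2-4, 40 in project months 49-54; last subject complete by project month 58 (year 5, month 10); analysis in project months 58-60. From section 9.2: 88 per arm, 0.36 SD, 20% dropout, correlation 0.5.

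**Assumptions.** Accrual is even within each period, and classes start without a wait after recruitment.

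**1. The plan's own figures.**
- Total: 39 + 3 × 47 + 40 = 220, as stated.
- Rate: 220 / (4.4 × 12) = 4.17 per month, in line with the stated average of about 4.
- Completers: 110 × 0.80 = 88 per arm, so only dropout is removed.
- Detectable difference: a baseline-adjusted comparison with correlation 0.5 gives (1.96 + 0.84) × √(2 × 0.75 / 88) = 0.37 SD, close to the stated 0.36.

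**2. The last subject.** Recruited in project month 54, this subject reaches month 12 in project month 66, six months after year 5 ends.

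**3. Month 12 for the whole sample.** The latest usable start is the last visit month minus 12. Detectable differences scale the stated 0.36 by √(88/n).

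| Last usable visit | Latest start | Cannot reach month 12 | Can reach it, per arm | After 20% dropout | Detectable difference |
|---|---|---|---|---|---|
| Month 58 | Month 46 | 2/12 × 47 + 40 = 47.8 (21.7%) | 172.2 / 2 = 86 | 69 | 0.36 × √(88/69) = 0.41 SD |
| Month 60 | Month 48 | 40 (18.2%) | 180 / 2 = 90 | 72 | 0.36 × √(88/72) = 0.40 SD |

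On the baseline-adjusted complete-case formula, power at 0.36 SD falls from about 79% with 88 per arm to about 68% with 69.

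**4. Month 6.** With a month-58 cut-off, the latest start is month 52. Those recruited in months 53-54 number 2/6 × 40 = 13.3, about 6% of 220. With a month-60 cut-off, none are lost.

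**5. If only MRI participants attend month 12/24.** This assumes that they accrue in the same pattern as the whole sample.
- Month-58 cut-off: 55 × 172.2/220 = 43 per arm, and 34.4 after 20% dropout. The detectable difference is 0.36 × √(88/34.4) = 0.58 SD.
- Month-60 cut-off: 55 × 180/220 = 45 per arm, and 36 after dropout. The detectable difference is 0.36 × √(88/36) = 0.56 SD.

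**6. Week 12.** The last recruit (project month 54) reaches week 12 by about project month 57 if classes start at once, before the month-58 cut-off.

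**The case against.** The best defence is that the timeline is simply out of date. Section 6 says the month-12 visit was added later, and Table 1 mentions only 6-month follow-up. That may explain the mismatch, although no text says so. It does not remove it, because the current section 4.3 still claims that the rate accommodates 12/24-month follow-up. The option of a month-24 visit does not help either, since it only moves the visit later.

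A second defence is that the mixed model uses all observed data, so late recruits still contribute earlier HAMD scores. This stands in part: the complete-case figures above are somewhat pessimistic for the planned analysis. The month-12 observations are still absent, and section 9.2 states its own power on complete data.

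A third is that little depends on month 12. The primary analysis is at week 12, maintenance is secondary, and 24-month follow-up is exploratory in a subset. This stands, and it limits the seriousness of the point.

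A reader might also infer more than the documents support:
- **That 22% is a minimum.** It depends on the month-10 cut-off and even accrual within year 4. The floor on this calendar is 40 of 220, or 18%.
- **That the calendar alone puts the trial below 88 per arm.** With visits to the end of year 5, 90 per arm can reach month 12 before dropout. The shortfall is established only once dropout is also applied.
- **That the loss is 27-29%.** This adds a wait of 3-4 months for everyone. Section 6.2.2 gives that wait as an upper limit counted from screening, and recruitment is not defined as screening.
- **That 86 per arm can replace 88.** It cannot while section 6 restricts the visit to MRI participants.
- **That late recruits will be counted as dropouts.** The plan is silent on this.

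**Conclusion.** The contradiction is real and lies within section 4.3. All 40 subjects recruited in year 5 (18%) miss month 12 even if visits run to the last day of that year. With the stated month-10 completion and even accrual, about 48 (22%) miss it, and about 13 miss month 6.

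The 88 complete cases per arm are not attainable under either reading of who attends. If everyone does, about 69-72 per arm remain after 20% dropout. If only MRI participants do, about 34-36 remain, provided they accrue evenly. The complete-case detectable differences rest on scaling the plan's own 0.36 SD by sample size.

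The week-12 primary analysis is not affected if classes start promptly. This is a point the sponsor should correct, not one that undermines the main comparison.

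**What to change.** 1. Reconcile Sample Size and Population and sections 4.3 (text and Table 1), 6, 9.2 and 9.5 on who has the month-12 visit and when follow-up ends. Do this before stating any replacement number.
2. Remove or correct the statement in section 4.3 that the rate accommodates 12/24-month follow-up.
3. Restate the month-12 sample size and detectable difference in section 9.2 for the number that the calendar allows, labelled as complete-case.
4. State in section 9.6 that subjects whose month-12 or month-6 visit falls after the data cut are administratively censored. Do not count them as dropouts in the drop-out comparisons or the pattern-mixture analysis.

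As an optional alternative, a later data lock for the month-12 aims alone would recover these visits and would delay only those results.

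The cost is wording and a less favourable stated 12-month figure. No extra patients are needed.

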5. STUDY INTERVENTIONS

5.1 Interventions, Administration, and Duration

Each class will be held for 60 minute per day/week. Homework assignments will be equal in all groups and ask for at least 20 minutes of either TCC, or computer searches on the topics of wellness at home. Participants will be asked to keep diaries of daily exercises, time spent and adherence to the tasks will be compared between the groups, and used as a predictor/mediator in the primary analyses of response. All classes will be offered once a month as booster session for the remainder of the study between weeks 12 and 24. Subjects will be given a DVD of the training course and encouraged to continue practice at home. Subjects in the HEW group will be asked not to join any of the TCC classes until the end of the study. At the end of the study, participants will be offered an option of participating in the two alternative classes.

Tai Chi Chih (TCC): TCC employs “meditation through movement” as a means of helping older adults cope with fatigue, perceived physical limitations, and negative emotional states, which are commonly associated with insomnia. Patients will be informed that TCC constitutes a health management intervention, which incorporates meditation and physical activity to promote a sense of well-being and control over negative symptoms associated with depression. The standard detailed protocol for TCC uses an adapted protocol from the “Tai-Chi-Chih Joy through movement” by Justine F. Stone¹⁴¹ and has been used in several studies by our research group, and others (i.e., R21-AT002307). TCC sessions will be held for 60 min a day once a week. Each class will allow 10 minutes of warm-up (e.g., stretching, breathing), 5 minutes of cool down. Participants will be instructed to practice at home for 20 minutes per day using handouts and documenting their practice in their daily diaries.

Health and Wellness Education (HEW) control group: This condition will serve as an active control for nonspecific treatment elements such as attention and group support that pose rival explanations for the effectiveness of TCC. Participants will be informed that this intervention is designed to help reduce the severity of depressive symptoms, and all participants will be offered a choice of TCC in the end of the interventions, to balance expectations for the TCC intervention; therefore, reducing the placebo effect. The PI and trained study staff will implement HEW using a manual that will present educational information and describe learning objectives and patient activities to promote integration of material. The detailed protocol for Health Education has been developed and used in the pilot project. The HEW sessions will be held once a week for 60 minutes over the 12-week treatment period. We will follow a didactic format, inviting experts to lecture on key topics, followed by focused group discussion, and post-discussion self-help quizzes to assess patient learning. This novel use of a non-exercise control intervention, which matches the exercise intervention in duration, frequency and social contact, represents an important methodological advance.¹⁴³ Participants will be instructed to practice at home in computer searches addressing the health topics discussed in the session for 20 minutes per day. Weekly supervision by [name] with project health education instructors will be used to monitor instructors’ adherence to the educational protocol. Tai Chi Chih trainers will follow the same manual. We will contact Tai Chi Chih Association for an opportunity to monitor TCC trainers’ adherence to the manual protocol. Participants will be asked to keep diaries of exercise or computer searches and the adherence will be compared between the groups.

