Interventions and Duration We anticipate screening about 500 subjects to recruit 220 older depressed adults (≥ 60 years old, all of whom will have a range of depressive symptoms and will be on stable treatment (antidepressant or psychotherapy) for at least 4 months. All will meet criteria for major depression and will be randomized to receive 12 weeks of TCC vs HEW used as an adjunct therapy to the stable antidepressant regimen. Follow-ups will confirm clinical endpoints of stable remission and the overall improvement in depression and cognition at Months 6 and 12 (or Month 24 if 12 months have already passed).

Interventions and Duration

Intervention 1 - Tai Chi Chih (TCC): TCC employs “meditation through movement” as a means of helping older adults cope with fatigue, perceived physical limitations, and negative emotional states, which are commonly associated with insomnia.

Intervention 2 - Health and Wellness Education (HEW) control group: This condition will serve as an active control for nonspecific treatment elements such as attention and group support that pose rival explanations for the effectiveness of TCC. Participants will be informed that this intervention is designed to help reduce the severity of depressive symptoms, and all participants will be offered a choice of TCC in the end of the interventions, to balance expectations for the TCC intervention; therefore, reducing the placebo effect.

Duration of Interventions: Each class will be held for 60 minute per day/week. Each TCC class will allow 10 minutes of warm-up (e.g., stretching, breathing), 5 minutes of cool down. Each HEW class will allow 5 min recap from the previous week and 10 min question and answer in the end of the lecture. Homework assignments will be equal in all groups and ask for at least 20 minutes of either TCC, or computer searches on the topics of wellness at home. Participants will be asked to keep diaries of daily exercises, time spent and adherence to the tasks will be compared between the groups, and will be used in the analyses of response.

Sample Size and Population

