6.2.3 Blinding

We have considered different options for blinding/masking procedures. We will provide treatment groups that both incorporate “exercise and wellness education,” which we believe will generate equal expectations for benefit. Both groups will be informed that they will receive exercise and education upon consent and entry into the study. Each group will have an option of trying and switching to the two other interventions after up to 24 months of follow up, which facilitates blinding and controls for the exercise effect. For ethical reasons, we cannot have a “usual care” group in which older depressed subjects at high risk for worsening of depressive symptoms in the absence of behavioral treatment. All subjects will be blind to the fact that symptomatic, functional and cognitive improvement are the outcomes of interest, and the differences in the interventions, since all participants will be recruited to receive a “wellness and exercise treatment program.”

Blind Assignment: The trained behavioral raters will also be “blind” to the treatment assignment.

Both statisticians and the PI will be blind to the group assignment. Only trainers and study coordinators will be unblinded, but they will not have access to the data monitoring or analyses. Database staff entering the data or managing the data will be blind to the treatment assignment. Groups in the documentation will be identified as 1 and 2. If unblinding occurs in the process of assessment, we will assign different raters who will continue to be unaware of the treatment group, and will re-establish reliability on all assessment instruments. We will minimize potential “placebo effects” by balancing expectations by introducing two “wellness and exercise” interventions for depression. We will measure and compare the expectancy for the outcomes at baseline, Week 12, Month 6 and Month 12 as specified below (or Month 24 if 12 months have passed). Both classes will be taught by different instructors. We will control for the “instructor” effect if several instructors teach classes.

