Aim 1: Primary analysis: Our primary analysis will consist of a GLMM for HAMD-24 with treatment group effects and time main effects, along with two-way interactions of time and group. The primary analysis will assess treatment effects at the end of treatment at 12 weeks. Our primary analysis is valid under the assumption of missing-at-random. To study missingness patterns, we will compare mean response trajectories of the primary outcome measure HAMD for subjects who dropped out and those who did not. We will further compare treatment groups for drop-out rates, time to drop-out and drop-out reasons. Since it is theoretically impossible to rule out data missing-not-at-random, we will also perform sensitivity analysis taking a pattern mixture approach. Our pattern mixture approach will make assumptions on how the outcome trajectory

for subjects who dropped out will differ from those for subjects who did not. These differences will be allowed to be vary across treatment arms and the amount of difference will be varied in a plausible range to obtain a full sensitivity analysis.

Secondary analysis: Treatment maintenance will be assessed via the GLMM at follow-up as part of the secondary analysis. Secondary analysis will also include comparison of remission status (binary outcome) at the end of treatment between treatment groups via a logistic regression. Analyses for secondary outcomes clinical global improvement (CGI) and cognitive domain scores in the executive function and memory domains will be similar to those above for the continuous HAMD scores. As noted in the Neuropsychological Assessment section, there are 4 cognitive domains that are being assessed. Of these, the two primary cognitive domains of interest for this proposal are executive function and memory. A separate GLMM as above will be estimated using these 2 domain scores as dependent variables. In addition treatment adherence and time in practice will be considered as moderators of treatment effects in the longitudinal modeling of primary depression and imaging outcomes in the first two aims.

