Aim 2. Hypothesis 2a, b: Primary analysis: Similar to Aim 1, the primary outcomes of DMN connectivity in rs-fMRI and BOLD activation during the mood task in the anterior cingulate will be modeled with a GLMM model with treatment group and time as main effects, along with their two-way interaction. Significant interactions would suggest differential trajectories over time for activation and connectivity outcomes in the two treatment groups. Primary analysis will assess treatment effects at 12 weeks in the primary outcomes. Sensitivity to missing data will be studied as explained in detail in Aim 1. The outcomes of DMN connectivity in rs-fMRI and BOLD activation will be treated as co-primary endpoints and further we will carefully examine the effect size of each co-primary endpoint to ensure clinically meaningful treatment effect.

Secondary analysis: Secondary measures for Aim 2 will be BOLD activation during the cognitive task in hippocampus. Secondary analysis will include assessment of treatment maintenance effects on the primary and secondary outcomes and of treatment effects during treatment in the secondary outcome of BOLD activation during the cognitive task in hippocampus.

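### The protocol gives inconsistent timings for offering Tai Chi Chih to the control arm, which leaves the secondary month-6 and month-12 contrasts open to crossover

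*Combined protocol and SAP*

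**What the plan says.** The combined protocol and SAP times the offer of TCC to control subjects in three ways.

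- **End of the interventions.** The HEW description in section 5.1 says "all participants will be offered a choice of TCC in the end of the interventions, to balance expectations for the TCC intervention". The Interventions and Duration text under Design and outcomes repeats it: "all participants will be offered a choice of TCC in the end of the interventions".
- **End of the study.** The opening paragraph of section 5.1 says "Subjects in the HEW group will be asked not to join any of the TCC classes until the end of the study". It then adds that the alternative classes will be offered when the study ends. It does not date that point. The same paragraph says "All classes will be offered once a month as booster session for the remainder of the study between weeks 12 and 24".
- **Up to 24 months.** Section 6.2.3 says "Each group will have an option of trying and switching to the two other interventions after up to 24 months of follow up".

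On the analysis side, Hypothesis 1 in section 1.1 compares the arms at 12 weeks, 6 months and 12 months (or 24 months). Section 9.6 sets the order of importance: "The primary analysis will assess treatment effects at the end of treatment at 12 weeks", while for mood "Treatment maintenance will be assessed via the GLMM at follow-up as part of the secondary analysis", and for imaging "Secondary analysis will include assessment of treatment maintenance effects on the primary and secondary outcomes". Section 9.3 specifies ITT on all randomised subjects with baseline assessments.

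**The concern.** A maintenance contrast between TCC and HEW is informative about TCC only if HEW subjects have not been taking TCC. Staff following the HEW description could offer it at week 12. Staff following the first paragraph of section 5.1 could offer it at about month 6, if they take the end of the study from the booster sentence. Staff following section 6.2.3 could wait as long as 24 months. No passage says which governs.

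Some uptake is plausible if the offer comes early, because section 4.3 names free TCC and HEW classes for every enrolled patient as the incentive to participate. The plan would not reliably show how much occurred. Section 5.3 asks for alternate treatments to be reported at each visit, but its examples are other mind-body practices and outside care, not TCC provided by the study. Homework diaries stop at week 12 in the Appendix A schedule. Sections 2.2 and 8 propose controlling for later treatment, but that conditions on a choice made after randomisation and does not restore the randomised comparison.

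**Working it through.** **Step 1: which outcomes each timing exposes.**

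| Place | Timing of the offer | Follow-up contrasts exposed |
|---|---|---|
| Design and outcomes; section 5.1, HEW description | End of the interventions, most naturally week 12 | Month 6 and month 12 |
| Section 5.1, first paragraph, study end read as week 24 | About month 6 | Month 12 |
| Section 5.1, first paragraph, study end read as the last visit | After follow-up | None |
| Section 6.2.3, read as after the subject's last follow-up | Month 12 or 24 | None |

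Week 12 is an inference. It rests on the 12 weeks of TCC or HEW stated under Design and outcomes, the 12-week treatment period in the HEW description, the 12 classes in section 6, and section 9.6, which places the end of treatment at 12 weeks.

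**Step 2: reproduce the plan's follow-up figure.** Section 9.2 gives 88 completers per arm (110 × 0.8), alpha 0.05, correlation 0.5 and a detectable d of 0.36 at 80% power. Sidedness is not stated; two-sided is assumed. For a baseline-adjusted comparison:

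- Residual SD = √(1 − 0.5²) = 0.866
- SE = 0.866 × √(2/88) = 0.1306
- Detectable d = (1.960 + 0.842) × 0.1306 = 0.366
- Power at d = 0.36 = Φ(0.36/0.1306 − 1.960) = Φ(0.797) = 78.7%

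This agrees with the stated 0.36 and 80% to within rounding and model choice. Below, the calculation is scaled so that d = 0.36 gives exactly 80% (implied SD 0.852).

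**Step 3: dilution.** Let u be the share of HEW subjects who take up TCC before the outcome, and e the share of the TCC effect they gain. Then

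- observed d = d × (1 − u·e)
- power = Φ(2.802 × (d/0.36) × (1 − u·e) − 1.960), with 88 per arm

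The documents give neither u nor e, so both are assumptions.

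| True d | u | e | Observed d | Power |
|---|---|---|---|---|
| 0.36 | 0 | – | 0.36 | 80% |
| 0.36 | 10% | 1 | 0.324 | 71% |
| 0.36 | 10% | 0.5 | 0.342 | 76% |
| 0.36 | 25% | 1 | 0.270 | 56% |
| 0.36 | 25% | 0.5 | 0.315 | 69% |
| 0.65 | 10% | 1 | 0.585 | 99.5% |
| 0.65 | 25% | 1 | 0.488 | 97% |
| 0.65 | 25% | 0.5 | 0.569 | 99% |

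Worked line: u = 10%, e = 1 gives 2.802 × 0.9 = 2.522, and Φ(2.522 − 1.960) = Φ(0.562) = 71%.

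The value 0.65 is the pilot effect at 12 weeks quoted in section 9.2. At that effect power is not the problem, but the estimate still shrinks by the factor 1 − u·e.

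**The case against.** The strongest reply is that an operative rule already exists. Section 5.1 bars HEW subjects from TCC classes until the study ends and, in the next sentence, times the offer to that point; section 6.2.3 is in keeping with this. The conflicting wording sits in a sentence about balancing expectations and names no visit. A specific bar would normally prevail over a loose description. This stands as evidence of intent: a reader might infer that the protocol plans a crossover at week 12, and the documents do not support that. It does not remove the inconsistency. The bar itself is undated, and the booster sentence beside it invites a week-24 reading.

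It can also be said that monthly boosters to week 24 mean the interventions do not clearly end at week 12. That is fair, and is why week 12 is called only the most natural reading.

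The illustration can be challenged too. Uptake is assumed, and full benefit is doubtful for month 6, because section 2.2 says that participants needed 12 weeks to master TCC and no TCC course for HEW subjects is scheduled during follow-up. The half-benefit rows are there for that reason. The 0.36 is a detectable difference, not an expected effect.

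Under a treatment-policy reading of ITT, dilution is part of what is estimated and should not be called bias. That is correct; it is bias only for the effect of TCC against HEW without crossover, and the plan does not say which effect the maintenance analysis targets.

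Finally, the physical activity record in section 6.2 might pick up some TCC practice, but it is not described as identifying TCC use or dating its start.

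**Conclusion.** The inconsistency is real and nothing in the documents resolves it. Followed as written, the end-of-interventions wording opens the month-6 and month-12 contrasts to crossover; a week-24 reading of study end opens month 12 only. Under ITT the difference shrinks by the product of uptake and benefit. The direction towards zero assumes that TCC is better than HEW, which is the trial's own hypothesis.

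The size cannot be computed from the documents. The figures above show sensitivity at chosen values of u and e and do not forecast a loss of power.

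Two stronger readings should be set aside. A reader might infer that the main result is compromised; it is not, because the primary contrast is at week 12, before any of these offers takes effect. A reader might also infer that the month-6 contrast needs relabelling because of booster access; boosters are offered for all classes, and that does not follow from this inconsistency.

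**What to change.** State one rule in the Interventions and Duration text under Design and outcomes, in both places in section 5.1, and in section 6.2.3: HEW subjects are offered TCC only after their last analysed outcome visit. That is month 12, or month 24 where it is used instead, and month 6 for anyone with no later visit. Define the end of the study for each subject in the same terms, so that the booster sentence cannot be read as setting it at week 24.

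In section 5.3, add TCC use by HEW subjects to the items reported at each visit, with its start date, so that any crossover can be counted and described alongside the maintenance results.

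The cost is wording in those places and one date field. Sample size, visits and model do not change. The drawback is a longer wait for TCC among HEW subjects, which may cost some retention.
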